### Physician Outcomes:

Physicians completed short background and baseline surveys to collect demographics and prior SDM training experience. They were also asked to review a list of their patients before being randomized into the study. Further, physicians completed a telephone-based SPI before staff started to enroll their patients. Lastly, once patient enrollment was complete, all physicians participated in a debrief interview.

- Background physician survey: Items assessed the number of years the physician had been in clinical practice, years working at their current site, and clinical sessions each week, as well as age, race, ethnicity, specialty, gender, and contact information. Additionally, physicians reported any prior formal training in SDM (and defined what that experience was).
- Baseline physician survey: Items assessed attitudes towards colonoscopy, stool-based tests, and not screening patients in this age group, subjective norms, and behavioral intention to engage their older adults in decisions about CRC screening. Physicians also completed the knowledge items and the physician's reactions to uncertainty scale.
- Simulated patient interaction: Physicians in both arms completed a telephone-based SPI before patient enrollment started. Intervention arm physicians complete the SPI after the SDM training. The SPIs were audio recorded and professionally transcribed, de-identified, and coded by two trained coders, who were blinded to the physicians' assignment. Coding followed the well-validated Braddock's Informed Decision Making framework to assess for presence of SDM elements.
- Post-visit survey: Physician participants completed a short online survey via REDCap after each eligible patient visit. The survey contained the SDM Process items adapted for physicians as well as an opportunity to provide a reason for not discussing CRC screening.

• Debrief interview: After patient recruitment was complete, research staff conducted a brief interview with participating physicians that followed a structured interview guide to assess physicians' attitudes toward SDM, their perceptions of the study, and satisfaction with the intervention, and ideas for improvement.

*Sample Size*: The study was powered to detect a small to medium effect size difference in the primary outcome, SDM process score. With 500 surveys (250 per arm), assuming an intraclass correlation coefficient of 0.03, the effective patient sample size was estimated at 394, which would enable detection of a difference of 0.28 standard deviations with 80% power and a two-sided significance level of 0.05.

*Statistical methods*: Responders and non-responders were compared to examine potential non-response bias using two-sample t-tests or chi-square tests. Patient sample characteristics were compared between arms using two-sample t-tests or chi-square tests. Multivariable regression models were used to adjust for potential effects of any unbalanced variables.

The following hypotheses were evaluated using an intention to treat approach, and patient outcomes were analyzed based on their physicians' assigned arm regardless of whether the physician completed the training, received the reminder, or discussed CRC screening.

 Examine the effects of the interventions on patients' SDM Process scores and knowledge score:

- a. Compared to the Comparator group, patients seen by physicians in the Intervention arm would report higher SDM Process scores (primary outcome) : We will examine the distribution of the SDM Process score and apply variable transformation techniques if necessary. We will use linear regression models with the Generalized Estimating Equations (GEE) techniques to account for the patients within clinician data structure. We will be able to difference of 0.28 SD for the SDM Process score with 80% power. Studies using the SDM Process survey have found effect sizes ranging from 0.39SD – 0.88SD when comparing sites that used have formal decision support (coaching or decision aids) and those that did not. Although we have sufficient power to detect a smaller difference, we are interested in a meaningful difference 0.4SD or higher.
- b. Compared to the Comparator group, patients seen by physicians in the Intervention arm would have greater knowledge: We will use linear regression with GEE to compare the mean knowledge score between the two arms. The target sample size will provide 80% power to detect a difference of 0.28 SD for the knowledge scores after adjusting for the effects of clustering. Although there are no standards for a minimally important difference in knowledge, SDM studies have found effect sizes of 0.25SD-0.8SD in studies of decision aids, and this study is adequately powered to detect a meaningful difference in that range, and
- Examine the effects of the interventions on patients' preferences for screening, the extent to which patients receive their preferred approach to screening, and on CRC screening rates.

- a. Compared to the Comparator group, patients seen by physicians in the Intervention arm will receive their preferred approach to screening (either colonoscopy, stool-based test, or no further screening). For these analyses, we will compare the percentages of patients who prefer to stop screening, the percentages of informed patients who received their preferred screening in the 12 months after the visit, and overall rates of screening across the two groups using logistic regression model with the GEE approach to adjust for clustering of patients within clinicians. We will have 81% power to detect a difference of 14% in rates (e.g. decrease from 61% to 47%).
- b. Both interventions will reduce screening rates compared to concurrent controls (rates of clinicians not involved in study). The screening data will be available for all patients from all participating sites. We estimate a total of 6248 patients will be eligible for screening from 436 clinicians: 5353 patients from clinicians not participating the study and 448 from each arm of clinicians participating the study. After taking into account clustering effect, we will have at least 86% power to detect a 6% decrease in CRC screening rates of patients from clinicians participating.
- 3. Examine the effects of the interventions on physicians' confidence and demonstration in their SDM skills and their satisfaction.
  - a. Compared to the Comparator group, physicians in the Intervention arm will report higher confidence in their SDM skills: Clinician confidence will first be analyzed as a continuous variable. Variable transformation will be performed to improve normality assumption if deemed necessary. Additionally, we will dichotomize the

variable into very or extremely confident vs. not. A two-sample t-test or Wilcoxon rank sum test, as appropriate, will be used to compare the continuous outcome while a chi square test will be used to compare the dichotomized outcome. With a sample size of 50 clinicians, we will have 81% power to detect difference of 35%, e.g. from 50% to 85%, in the percentage of clinicians who are very or extremely confident in different elements needed to conduct SDM conversations. In our prior study of the SDM skills webinar, we found a 30-40% absolute increase in clinician confidence.

- b. Compared to the Comparator group, physicians in the Intervention arm will demonstrate more SDM skills in the SPI: We will code each transcript using Braddock's Informed Decision Making framework that covers core aspects of SDM (scores range from 0 to 9). First, we will determine whether a two-sample t-test or a Wilcoxon rank sum test is more appropriate to compare the two groups. Assuming the score is normally distributed, a sample size of 25 in each group will have 80% power to detect a 0.81SD difference in the mean Braddock score (or about 1.4 points out of 9). Our prior study of a 3-hour CME online SDM skills webinar, we found an increase of 1.2SD on the Braddock scale after training.
- c. Compared to the Comparator group, physicians in the Intervention arm will report higher satisfaction with the visit. The percentage of clinicians who report that they are extremely satisfied with the visit will be compared across arms using a chisquare test.
- 4. Examine the effects of the interventions on **caregivers' SDM Process scores**: Caregivers who attended a visit with an eligible patient (and for whom the patient provided contact

information) were invited to complete a post-visit survey. They were asked to complete an adapted version of the SDM Process survey to provide their perspective on the conversation and involvement of the patient. A total score will range from 0-4, with higher scores indicating more shared decision making. These analyses are exploratory.

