We will conduct a comparative effectiveness trial that will randomly assign clinicians at participating academic and community practices to one of two different decision support strategies. The first strategy (Registry arm) takes a population health management (PHM) approach and uses a patient registry to identify and track use of CRC screening among older adults for each clinician. The second strategy will enhance the registry by adding an established, multi-faceted SDM training program for clinicians (SDM Skills arm). We will enroll patients of participating primary care providers (PCPs), aged 76-85, who are due or overdue for CRC screening, and survey them shortly after an office visit to determine the impact of the two strategies on outcomes of importance to patients. We plan to randomly assign about 60 participating PCPs to the SDM skills or Registry arms, and enroll about 500 of their eligible patients. We will compare reports of shared decision making, patients' knowledge, and rates of patients who get their preferred option for CRC screening across study arms. We will also compare CRC screening rates across arms and to concurrent and historical controls. Through this project, we will accomplish the following specific aims:

Aim 1: Determine the impact of the approaches on patients' involvement in decision making and knowledge about the risks and benefits of continued CRC screening.

Hypothesis 1.1 (Primary outcome): Patients seen by clinicians in the SDM Skills arm will report more SDM discussions about cancer screening compared to the Registry arm.

Hypothesis 2.1 (Secondary outcome): Patients seen by clinicians in the SDM Skills arm will have higher knowledge of the benefits and harms of CRC screening and treatment compared to Registry arm.

Aim 2: Examine the effects of the interventions on patients' preferences for screening, the extent to which patients receive their preferred approach to screening, and on CRC screening rates.

Hypothesis 2.1 (Secondary outcome): A higher percentage of patients will receive their preferred approach to screening in SDM Skills arm compared to the Registry arm. Hypothesis 2.2: (Secondary outcome) Both interventions will reduce CRC screening rates compared to concurrent controls (rates of clinicians who are not involved in study).

Aim 3: Examine the impact of the interventions on physicians' confidence with and skills for SDM in this setting.

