- Clinicians in Registry arm will complete a baseline telephone-based simulated patient interaction to evaluate their SDM skills. Once patient enrollment begins study staff will send periodic notification of their patients aged 76-85 who are due for colorectal cancer screening with an upcoming visit.
- Clinician participants in the SDM arm will complete an online SDM skills course, two telephone-based simulated patient interactions, and monthly facilitated case-based discussions. Once patient enrollment begins, study staff will send periodic notification of their patients aged 76-85 who are due for colorectal cancer screening with an upcoming visit.

Study staff will use existing functionality in the electronic medical record (EMR) via RPDR and Epic Reports to generate a list of patients 75 and older with CRC screening status, prior CRC screening results, and upcoming visit dates for each participating clinician. Staff will also work within the EMR at each site to develop an automated report of these items as available.

Our target is to enroll approximately 10 patients per clinician for a total of 500 patients. The clinicians will complete a short survey after each eligible patient visit. The patients will be invited to participate in the survey study and will be asked to complete a survey after their visit and another short survey one year later. Patients will be asked whether a spouse, friend or caregiver was involved in the decision-making process and if so, whether they would be willing to invite them to participate in the study. Study staff will follow up to enroll caregivers that patient participants identify and administer a short survey. We expect that about half of the patients will identify a caregiver, so about 250 caregivers will be surveyed.

The research coordinator will track the number of study participation invitations sent to each clinician as well as the number of clinicians indicating interest. We will track any reason given for refusal to join the study as well as any reason for dropping out of the study after randomization for reporting in CONSORT flow diagram. Staff will track completion of each activity (baseline survey, simulated patient interaction, training course, etc) for each clinician participant.

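### Hypotheses 1a, 1b and 2a rely on GEE with only about 50–60 clinicians and no small-sample correction; under default inference the nominal 5% test would run at about 6–7%

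*SAP*

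**What the plan says.** Under Statistical methods in the SAP, three hypotheses are tested by GEE with patients clustered in clinicians:

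- 1a, SDM Process score (primary): "We will use linear regression models with the Generalized Estimating Equations (GEE) techniques to account for the patients within clinician data structure".
- 1b, knowledge: "We will use linear regression with GEE to compare the mean knowledge score between the two arms".
- 2a, preference to stop, receipt of the preferred approach, and overall screening: "using logistic regression model with the GEE approach to adjust for clustering of patients within clinicians".

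The SAP's Sample Size paragraph sets a two-sided 5% level. It assumes 500 surveys and an ICC of 0.03, and gives an effective sample of 394 and a detectable difference of 0.28 SD at 80% power.

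The number of clusters is small wherever it is given. The protocol's Specific Aims state: "We plan to randomly assign about 60 participating PCPs to the SDM skills or Registry arms". Its description of study procedures implies 50: "Our target is to enroll approximately 10 patients per clinician for a total of 500 patients". The clinician-level power statement in SAP hypothesis 3a begins "With a sample size of 50 clinicians". That hypothesis is not itself a GEE analysis; it is cited only for the count.

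Neither document states the variance estimator, the working correlation, the reference distribution or a small-sample correction for any GEE analysis.

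**The concern.** A GEE analysis with nothing further specified is ordinarily run with the uncorrected sandwich standard error and a normal reference. Both are large-sample devices, and the relevant sample is the number of clusters: 25 to 30 per arm here, not 250 patients per arm. With so few clusters the uncorrected sandwich variance is biased low, and the normal critical value ignores the error in estimating it. Both push the test above its nominal level and make intervals too short. Unequal numbers of patients per clinician add to the effect, as would clinician-level covariates.

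At stake is a borderline primary result. A p-value just under 0.05 by the default could exceed 0.05 by a test that holds its level. Because the SAP is silent, the choice between the two also remains open after the data are seen.

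**Working it through.** **Inputs.** From the SAP: 500 patients, ICC 0.03, two-sided 5%, 0.28 SD, and K = 50 clinicians. From the protocol: K about 60, and about 10 patients per clinician. Variation in cluster size, the share of variance explained by strata, and the number of covariates are not in the documents and are assumed below.

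**The plan's own figure.** Design effect 1 + (10 − 1) × 0.03 = 1.27, so the effective sample is 500/1.27 = 393.7, matching the stated 394. With 197 per arm, normal-theory power for 0.28 SD is 79.4%, matching the stated 80%. The figure therefore rests on 10 patients per clinician, that is, 50 clusters. With 60 clusters the mean size is 8.33, the design effect 1.22, and the effective sample 409.8.

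**Level of the default test, equal clusters, no covariates.** With c = K/2 clinicians per arm, the GEE estimate is the difference between arm averages of clinician means. The uncorrected sandwich divides by c where an unbiased variance divides by c − 1. The default test therefore rejects when |t| with K − 2 df exceeds 1.96 × √((c − 1)/c).

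- K = 50: 1.96 × √(24/25) = 1.920; P(|t48| > 1.920) = 6.1%.
- K = 60: 1.96 × √(29/30) = 1.927; P(|t58| > 1.927) = 5.9%.

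**Interval width relative to a valid interval.**

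- K = 50: (1.960/2.011) × √(24/25) = 0.955.
- K = 60: (1.960/2.002) × √(29/30) = 0.963.

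**Simulation under the null.** Linear GEE, exchangeable, 500 patients, ICC 0.03, 6,000 replicates per row, Monte Carlo SE about 0.3 points. Entries are the percentage rejected at nominal 5%.

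| Clinicians | Size CV | Outcome and model | Uncorrected, normal | Kauermann-Carroll, t | Mancl-DeRouen, t |
|---|---|---|---|---|---|
| 50 | 0 | normal, arm only | 6.2 | 5.1 | 4.7 |
| 50 | 0.5 | normal, arm only | 6.8 | 5.5 | 4.9 |
| 50 | 0.8 | normal, arm only | 7.8 | 6.4 | 5.6 |
| 60 | 0 | normal, arm only | 5.7 | 5.0 | 4.6 |
| 60 | 0.5 | normal, arm only | 6.1 | 5.1 | 4.7 |
| 60 | 0.8 | normal, arm only | 7.1 | 5.8 | 5.2 |
| 50 | 0.5 | discrete 0–4 score, arm only | 6.8 | 5.5 | 4.8 |
| 60 | 0.5 | discrete 0–4 score, arm only | 5.9 | 4.9 | 4.5 |
| 50 | 0.5 | normal, five clinician-level covariates | 8.7 | 5.6 | 3.8 |
| 60 | 0.5 | normal, five clinician-level covariates | 8.7 | 6.0 | 4.4 |

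A run with 50 clinicians, five clinician-level covariates and CV 0.8 gave about 10.7%, but some replicates failed numerically and I do not rely on it. A separate simulation on clinician means, arm only, gave 6.4–6.7% for 50 clinicians and 5.6–6.5% for 60 over CV 0 to 0.8. Logistic GEE with 50 clinicians and CV 0.6 gave 7.4% (Monte Carlo SE 0.7).

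**Effect of stratified randomization, K = 50, equal clusters.** With outcome variance 1, a clinician mean has variance 0.03 + 0.97/10 = 0.127. If strata explain a share s of the 0.03 and are left out of the model, the true variance is proportional to 0.127 − 0.03s while the model still estimates 0.127. The threshold becomes 1.920/√((0.127 − 0.03s)/0.127).

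- s = 0.2: 1.967, level 5.5%.
- s = 0.3: 1.992, level 5.2%.
- s = 0.5: 2.045, level 4.6%.

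**Price of a valid test.** For K = 50 the standard error is √(2 × 0.127/25) = 0.1008 SD. Power for 0.28 SD goes from 79.4% (normal) to 77.7% (t with 48 df). For K = 60 it goes from 80.9% to 79.6%. The detectable difference for K = 50 goes from (1.960 + 0.842) × 0.1008 = 0.282 to (2.011 + 0.849) × 0.1008 = 0.288 SD.

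**The case against.** A reader might infer that the trial's true type I error is 6–9% and that every GEE p-value and interval is anti-conservative. The documents do not support that, for three reasons.

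First, the SAP does not say that it uses the uncorrected standard error with a normal reference; it says nothing. The inflation is conditional on the default being followed.

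Second, the 8–9% end needs several clinician-level covariates. The SAP's sentence on multivariable adjustment follows directly on a comparison of patient characteristics between arms, and nothing says that the stratification factors enter the model. With four patient-level covariates instead, a 4,000-replicate simulation (Monte Carlo SE about 0.4 points) gave 5.6–6.4%, no visible increase over the 5.4–6.3% found without covariates.

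Third, the SAP randomized within strata of gender, years in practice, prior SDM training and site. If these explain between-clinician variance, an unadjusted analysis is pulled back towards 5% or below it.

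It can also be said that little turns on this in practice. A result at p = 0.05 corresponds to about 1.96 × 0.1008 = 0.20 SD, while the SAP calls 0.4 SD or more meaningful. A 5% change in interval width would not alter a conclusion at 0.4 SD.

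All of this stands, and it limits the size of the point. It does not remove it. Significance is still declared at 5%, the strata's contribution is unknown, and the plan as written permits a test that exceeds its level when a standard one would come close to holding it.

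**Conclusion.** The point holds in a modest, conditional form. Hypotheses 1a, 1b and 2a use GEE on about 50–60 clusters without a small-sample correction. Under the ordinary default, the nominal 5% level would be about 6–7% without covariates, and equal-cluster intervals about 4–5% too narrow. One linear run with very unequal clusters (CV 0.8, 50 clinicians) reached 7.8%. The level would be somewhat lower if omitted strata explain between-clinician variance, and about 9% only with several clinician-level covariates.

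The analytic figures rest on equal clusters and default inference. The rest depends on assumed cluster-size variation, stratum effects and covariate numbers. Logistic GEE for 2a was checked in one setting only. Hypothesis 2b draws on 436 clinicians and is outside this point.

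**What to change.** In SAP hypotheses 1a, 1b and 2a, specify three things:

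- an exchangeable working correlation;
- a bias-corrected sandwich standard error, for example Kauermann-Carroll or Mancl-DeRouen;
- a t reference with degrees of freedom equal to the number of clinicians minus the number of clinician-level parameters.

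Use these for the primary p-value and for all reported intervals. Either estimator is acceptable. In the arm-only runs tabulated above, Kauermann-Carroll gave 4.9–6.4% and Mancl-DeRouen 4.5–5.6%. With five clinician-level covariates Mancl-DeRouen was conservative (3.8–4.4%) and Kauermann-Carroll slightly liberal (5.6–6.0%). What matters is that one is named.

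The cost is one sentence and a standard software option. Intervals widen by about 5% (1/0.955 = 1.047 for 50 clinicians). Power for 0.28 SD falls by about 1–2 points, and the detectable difference becomes about 0.29 SD. No new data are needed. The SAP is dated after patient enrollment closed, so if the analyses have already been run, they can be repeated on the same data.

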### Patient Outcomes:

- Screening uptake: study staff examined medical records to determine receipt of any colorectal cancer screening test for all subjects within 12 months of the index visit.
  The following measures were collected in the patient survey:
  - SDM Process Scale: This 4-item measure assessed the discussion of 1) stopping screening as an option, 2) reasons to screen, 3) reasons not to screen, and 4) patients' screening preference. Individual items were summed to generate a total score (0-4), with higher scores indicating greater shared decision making. Score was calculated if all 4 items were answered and patients who indicated no discussion of CRC received a score of 0.
  - Risk perceptions: One item assessed affective risk perception, or cancer worry. This item will be adapted from the National Cancer Institute's Health Information National Trends Survey (HINTS).
  - Knowledge: Seven multiple choice knowledge items, adapted from the Colorectal Cancer Screening Decision Quality Instrument, were scored. A total knowledge score (0-100%) were calculated if at least half of the knowledge items (4 or more) were answered with the missing items considered as incorrect.

- Screening preference: One item asked patient's preferred approach to screening (with responses: colonoscopy, stool-based test, no screening, and not sure).
- Overall health: patients self-reported overall physical and mental health (PROMIS Scale v1.2-Global Health Physical 2a (poor to excellent).
- Patient's screening intention: One item assessed how likely the patient was to follow through with their preferred approach on a 5-point scale from Definitely will to Definitely will not.
- Screening recommendation and time spent: One item will assess the physician's recommendation about CRC screening (colonoscopy, stool-based test, no further testing, other) and one item will assess if time was spent discussing CRC screening in the visit (yes/no) and if discussed, how much time was spent (<2 minutes, 2-5 minutes, > 5 minutes).
- Single item literacy screener: reported as percentage who never or rarely require help reading medical information indicating high health literacy
- Satisfaction: One item asked "Overall, how satisfied were you with the visit" on a 4-point scale from Extremely satisfied to Not at all satisfied.

Additional data were collected to describe the sample including

- Demographics: race, ethnicity, employment, marital status and education

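### SAP hypothesis 2a concerns all patients, but its only analysis of receiving the preferred approach counts 'informed' patients, an undefined group that training is meant to enlarge

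*SAP*

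**What the plan says.** The hypothesis is worded for all patients in three places:

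- Protocol, Specific Aims, Aim 2, Hypothesis 2.1: "A higher percentage of patients will receive their preferred approach to screening in SDM Skills arm compared to the Registry arm".
- SAP, Statistical methods, aim 2 heading: "the extent to which patients receive their preferred approach to screening, and on CRC screening rates".
- SAP, Statistical methods, item 2a, hypothesis sentence: Intervention-arm patients "will receive their preferred approach to screening (either colonoscopy, stool-based test, or no further screening").

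Item 2a then plans three logistic GEE comparisons: the share who prefer to stop screening, "the percentages of informed patients who received their preferred screening in the 12 months after the visit", and overall screening rates. Only the second measures whether a preference was met, and it alone carries the word 'informed'.

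The obvious basis for 'informed' is the knowledge measure. Under Patient Outcomes the SAP says: "A total knowledge score (0-100%) were calculated if at least half of the knowledge items (4 or more) were answered". Missing items count as incorrect, but no score is named above which a patient is informed. The protocol's 0-5 knowledge score has no cut-off either.

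The SAP places its hypotheses under intention to treat, by the physician's assigned arm. It gives 81% power in item 2a for a 14-point difference (61% to 47%).

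**The concern.** The clause can be read in two ways.

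**Subset.** The denominator is informed patients. The survey is completed after the visit, so this conditions on something measured after randomisation that the training is intended to change. If 'informed' means the knowledge score, item 1b expects that "patients seen by physicians in the Intervention arm would have greater knowledge". If it means the SDM Process score, item 1a expects that "patients seen by physicians in the Intervention arm would report higher SDM Process scores". The informed patients in the two arms are then different kinds of patients, and their receipt rates can differ even when training changes nobody's receipt.

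**Composite.** The numerator is informed and received, over all patients. The randomised groups stay intact, but a gain in knowledge alone moves the result.

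On either reading the figure reported for this secondary hypothesis can depart from the effect on receipt, and a reader could not tell which quantity had been estimated. Timing adds to this. The SAP is dated July 27, 2022, about three months after 12-month follow-up of the last patients (enrolled April 2021) would have ended, so any cut-off chosen now is chosen with the data already collected.

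A smaller gap sits alongside. Item 2a names three approaches, but the preference item has a fourth response, 'not sure', with no rule for handling it.

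**Working it through.** **1. The plan's own power figure.** Inputs from the SAP Sample Size paragraph: 500 surveys (250 per arm), ICC 0.03, two-sided 0.05. About 10 patients per clinician comes from the protocol's design section.

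- Design effect = 1 + (10 - 1) x 0.03 = 1.27; 500 / 1.27 = 393.7 (SAP: 394), or 197 per arm.
- Power for 61% vs 47% at 197 per arm: 80.4% (unpooled variance), 79.8% (pooled). The stated 81% is reproduced to within rounding and choice of method, and it uses every surveyed patient.

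**2. Model for the two readings.** The documents give no share informed, no base rate for preferred receipt and no correlation between them, so these are assumptions. Let being informed (probability pI) and receiving the preference (pR) be cut-points on two normal variables with correlation r.

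- Composite rate = Phi2(z(pI), z(pR); r).
- Subset rate = composite rate / pI.

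Set pR = 0.61 in both arms, so the true effect is zero, and pI = 0.50 in the Comparator arm. A knowledge shift of d SD gives pI = Phi(d) in the Intervention arm: 0.599 at 0.25, 0.610 at 0.28 and 0.788 at 0.8. The 0.28 is the SAP's detectable difference, not an expected effect. The other two are the ends of the range in item 1b: "SDM studies have found effect sizes of 0.25SD-0.8SD in studies of decision aids".

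**3. False difference, Intervention minus Comparator (percentage points).**

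| Shift | Reading | r = -0.2 | r = 0 | r = 0.1 | r = 0.5 |
|---|---|---|---|---|---|
| 0.25 SD | subset | +1.2 | 0 | -0.6 | -2.8 |
| 0.28 SD | subset | +1.35 | 0 | -0.6 | -3.1 |
| 0.8 SD | subset | +3.4 | 0 | -1.6 | -8.4 |
| 0.28 SD | composite | | +6.7 | | +6.6 |
| 0.8 SD | composite | | +17.6 | | +15.6 |

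Example, composite at r = 0 and 0.28 SD: 0.610 x 0.61 - 0.50 x 0.61 = 0.372 - 0.305 = +6.7 points.

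Sensitivity at 0.28 SD:

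- With 20% to 80% informed in the Comparator arm, the subset figure is -0.4 to -3.2 (r = 0.1 to 0.5) and the composite +2.8 to +7.3 (r = 0 to 0.5).
- With receipt of 40% to 80%, the composite is +3.9 to +9.0.

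**4. Against sampling error.**

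- Effective informed patients per arm = 250f / (1 + (10f - 1) x 0.03), where f is the share informed: 111.6 at f = 0.50 and 132.3 at f = 0.61.
- Subset: the standard error at 61% is 6.3 points (6.0 at 0.8 SD), so the 0.28 SD bias is at most about half a standard error.
- Composite at r = 0: the standard error is about 4.8 points, so +6.7 is about 1.4 standard errors. The chance of a significant result with no change in receipt is about 29% at 0.28 SD and 95% at 0.8 SD.

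**5. Power for 14 points (unpooled).**

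| Rates | Full sample (197 per arm) | Informed only (112 vs 132) |
|---|---|---|
| 61 vs 47 | 80.4% | 59.9% |
| 50 vs 64 | 80.9% | 60.2% |
| 66 vs 80 | 88.7% | 69% |

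**6. 'Not sure'.** Assume 20% (Comparator) and 10% (Intervention) are not sure, and 61% of decided patients in each arm receive their preference.

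- Coded as 'no': 0.90 x 0.61 - 0.80 x 0.61 = +6.1 points. Excluded: 0.
- If the extra 10% who become decided receive theirs at 30%, the Intervention rate coded 'no' is 0.80 x 0.61 + 0.10 x 0.30 = 0.518, against 0.488, or +3.0. Excluded, it is 0.518 / 0.90 - 0.61 = -3.4.

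**The case against.** The best reply is that 'informed' is loose wording. The hypothesis sentence, the aim heading and the protocol all say patients, and the intention-to-treat sentence covers item 2a, so an all-patient denominator may be intended. That is possible. But intention to treat fixes the arm; it neither defines 'informed' nor states who is counted. Reading the clause that way means deleting the word, which is the correction asked for.

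Several narrower points stand:

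- The SDM Process score is a less natural meaning of 'informed' than the knowledge score, since the documents treat being informed and being involved as separate things.
- The 81% power sentence is not wrong. Its example, a fall from 61% to 47%, looks like a screening-rate comparison, and the SAP does not claim it for a subset. The point is only that it should not be carried over to one.
- The sizes rest on assumed inputs. Subset bias is zero at zero correlation and small against sampling error at 0.28 SD. The largest figures use 0.8 SD, from decision-aid studies, whereas this trial tests clinician training.
- The 'not sure' rule is a separate, secondary matter.
- The analysing biostatistician was blinded, which limits a cut-off chosen to favour an arm. It does not supply a definition.

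A combined informed-and-concordant outcome can be legitimate if it is named and defined. It is not the hypothesis stated here.

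**Conclusion.** The concern holds and should be fixed. That the term is undefined, and that the analysis clause does not match the hypothesis, follows from the text alone and needs no assumption. The other two comparisons in item 2a do not fill the gap, because neither shows whether a preference was met.

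The size of the distortion is less certain because every input is assumed. At a modest knowledge gain the subset reading costs more in power than in bias. The composite reading is the more misleading, since it can credit training with better receipt when only knowledge improved. If informed patients are likelier to receive their preference, the two readings err in opposite directions. The matter is confined to one secondary hypothesis.

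**What to change.** Make the item 2a test the planned logistic GEE of receipt of the preferred approach within 12 months (yes/no), in all survey respondents by assigned arm.

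- State one rule for 'not sure' in advance, with a sensitivity analysis under the other coding. Each has a drawback: coding 'no' mixes indecision with non-receipt, and excluding creates another post-visit subset.
- If an informed-based result is kept, name its measure, fix the knowledge cut-off before analysis, state the denominator and label it supplementary (post hoc if already run).
- State that the 81% power for 14 points rests on the full effective sample of about 394 and does not apply to an informed-only comparison.

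The cost is SAP wording and one logistic GEE. No new data are needed, because survey completers already have 12-month follow-up.

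Limits remain. The all-respondent comparison still depends on who returned the survey and on a preference stated after the visit, so its advantage over the subset is one of degree.
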